##### **Adverse reaction (AR):**

All noxious and unintended responses to a medicinal study product (TG4050) related to any dose or to a study specific procedure.

#### Dose-limiting toxicity (DLT)

Any of the following treatment-emergent AE occurring during the first 6 weeks after TG4050 administration:

- any grade  $\geq 3$  toxicity that is at least possibly related to TG4050, with the following exception: pre-existing grade 2 fatigue at baseline that would worsen up to grade 3
- any death

The occurrence of one of those events in the initial 3 treated patients will trigger study hold.

Beyond the safety run-in phase, a dose-limiting toxicity is defined as any treatment-emergent AE grade  $\geq 3$  toxicity that is at least possibly related to TG4050, with the following exception: pre-existing grade 2 fatigue at baseline that would worsen up to grade 3.

In any case, patients experiencing a dose-limiting toxicity will discontinue study treatment permanently.

#### Serious adverse events

A **Serious Adverse Event (SAE)** is any untoward medical occurrence that at any dose:

- results in death
- is life-threatening (defined as an event in which the patient was at risk of death at the time of the event; it does not refer to an event which hypothetically might have caused death if it were more severe)
- requires inpatient hospitalization or causes prolongation of existing hospitalization (see NOTE below)
- results in persistent or significant disability/incapacity
- is a congenital anomaly/birth defect
- is an important medical event (defined as a medical event(s) that may not be immediately life-threatening or result in death or hospitalization but, based upon appropriate medical and scientific judgment, may jeopardize the patient or may require intervention (e.g., medical, surgical) to prevent one of the other serious outcomes listed in the definition above.) Examples of such events include, but are not limited to, intensive treatment in an emergency room or at home for allergic bronchospasm; blood dyscrasias or convulsions that do not result in hospitalization.) Potential drug induced liver injury (DILI) is also considered an important medical event

Suspected transmission of an infectious agent (e.g., pathogenic or nonpathogenic) via the study drug is an SAE.

Although overdose and cancer are not always serious by regulatory definition, these events must be handled as SAEs.

#### Suspected Unexpected Serious Adverse Reaction (SUSAR):

A SUSAR is any unexpected SAE considered as related to the study treatment or to a study specific procedure.

Expected adverse events are those adverse reactions that are listed or characterized in the reference document (e.g., IB).

Unexpected adverse reactions are those not listed in the reference document or not identified. This includes adverse events for which the specificity or severity is not consistent with the description in the SAP-template version of 4 Jan 2024

reference document.

### 8.10.1.2 AEs analysis

#### Adverse Events

AE summaries will include all TEAEs corresponding to AEs that have started on or after the day of first study treatment administration or that have worsened on or after first TG4050 administration and starting no later than 30 days after the date of last study treatment administration.

For these analyses, the number and percentage of patients with at least one AE will be summarized in a frequency table by System Organ Class (SOC) and Preferred Term (PT) as per MedDRA dictionary. The number of events will also be summarized in the same table. Tables will be presented by SOC sorted in alphabetic order and PTs within SOC sorted by descending number of counts according to the overall column.

Written narratives will be produced for all SAEs and unexpected or other significant AEs that are judged to be of special interest because of their clinical importance.

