#### **6.2.6. Safety Follow-up visit**

A safety follow-up visit will be performed at least 30 days (+14 days allowed) after the last dose of study treatment.

The following evaluations will be conducted and recorded in eCRF:

- Physical examination, including vital signs and weight
- PS on ECOG scale
- Adverse events reporting
- Concomitant medications
- Reporting of subsequent cancer therapy if applicable

For patients who refuse to return for a visit, they will be contacted by phone to obtain this information if possible.

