## 7.2. Treatment duration

Study treatment will be administered up to a total of 20 injections unless disease progression justifying initiation of further treatment, unacceptable toxicity including occurrence of a dose-limiting toxicity, or patient withdrawal due to any reason, whichever occurs first.

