## 9.3. Study endpoint

### 9.3.1. Primary endpoint

Adverse events will be assessed throughout the treatment period and graded according to NCI CTCAE version 5.

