##### **Treatment-emergent adverse Event (AE):**

A treatment-emergent adverse event (TEAE) is defined as a sign or symptom that emerges during treatment or within 30 days of the last dose of the study drug, having been absent pre-treatment or that has worsened relative to the pre-treatment state. Any adverse event deemed related to study drug will also be considered a TEAE regardless of elapsed time since last study drug dose.

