### 8.10.2 Laboratory abnormalities

The summaries will include all laboratory assessments collected from baseline assessment until 30 days after treatment discontinuation. All laboratory assessments will be listed and those collected more than 30 days after study treatment discontinuation will be flagged in the listings.

All laboratory values will be converted into SI units and will have a severity grade calculated using appropriate common terminology criteria for AEs (NCI-CTCAE, version 5). A listing of laboratory values will be provided by laboratory parameter and patient. A separate listing will display notable laboratory abnormalities (i.e., newly occurring CTCAE Grade 3 or 4 laboratory toxicities). The frequency of these notable laboratory abnormalities will be displayed by parameter. The shift tables using CTCAE grades to compare baseline to the worst post-baseline value will be produced for all relevant safety measures as described in the statistical analysis plan. Note that for parameters with two directions abnormalities (hypo/hyper), two tables will be presented.

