### 10.2 Listings

Listing number	Title
16.2	PATIENS DATA LISTINGS
16.2.1	Discontinued patients
Listing 16.2.1.1	Screen failure patients and non-inclusion reasons – SCR
Listing 16.2.1.2	Patients' disposition – SAF
16.2.2	Protocol deviation for enrolled patients
Listing 16.2.2.1	Protocol deviations at inclusion for treated patients – SAF
Listing 16.2.2.2	Protocol deviations during study for treated patients – SAF
16.2.4	Demographic data and Baseline characteristics by patient (enrolled patients)
Listing 16.2.4.1.1:2	Demographic and baseline characteristics: SCR/SAF
Listing 16.2.4.2.1:2	History of studied disease – SCR/SAF
Listing 16.2.4.3. 1:2	Prior Anti-Cancer Therapy: Medication – SCR/SAF
Listing 16.2.4.4.1	Relevant Medical History and current Medical Conditions – SAF
Listing 16.2.4.5.1:2	CA-125 concentration at study entry and during screening period – SCR/SAF
Listing 16.2.4.6	Signs and symptoms at baseline – SAF
Listing 16.2.4.7	Serology – SCR/SAF
16.2.5	Compliance and study conduct data
Listing 16.2.5.1	TG4050 administration – SAF
Listing 16.2.5.2	TG4050 administration per patient – SAF
Listing 16.2.5.3	Delayed, cancelled or stopped administration of TG4050 (Listing) – SAF
Listing 16.2.5.4	Discontinuation of study treatment and study (Table) – SAF
Listing 16.2.5.5	Prior and concomitant medications (on or after D1) – SAF
Listing 16.2.5.6	Prior and concomitant medications (before D1) – SAF
Listing 16.2.5.7	Further anti-cancer therapies – SAF
16.2.6	Individual efficacy response data by patient (enrolled patients)
Listing 16.2.6.1	CA-125 concentration during treatment period – SAF
Listing 16.2.6.2	Failure to treat/provide – SCR
Listing 16.2.6.3	Objective tumor assessments by evaluation – SAF
Listing 16.2.6.4	Detailed tumor assessment – SAF
Listing 16.2.6.5	Time to measurable relapse / Time to Progressive Disease – SAF
16.2.7	Adverse event listings by patient
Listing 16.2.7.1	Adverse events – SAF
Listing 16.2.7.2	Adverse events related to TG4050 – SAF
Listing 16.2.7.3	Serious Adverse events before treatment – SAF
16.2.8	Listing of individual laboratory measurements by patient

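### All-cause TEAE tables run to 30 days after the last TG4050 dose without flagging events that start after the next anticancer therapy, so second-line toxicity can enter them

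*SAP*

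**What the plan says.** The primary endpoint in Protocol 9.3.1 is all-cause: "Adverse events will be assessed throughout the treatment period and graded according to NCI CTCAE version 5". SAP 8.10.1.2 implements it as follows: "AE summaries will include all TEAEs corresponding to AEs that have started on or after the day of first study treatment administration", or that worsened from then on, "starting no later than 30 days after the date of last study treatment administration". Protocol 9.4.1 has the same rule. The SAP's TEAE definition (8.10.1.1) adds a provision for late related events: "Any adverse event deemed related to study drug will also be considered a TEAE regardless of elapsed time since last study drug dose".

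Protocol 7.2 allows up to 20 injections "unless disease progression justifying initiation of further treatment", unacceptable toxicity or withdrawal comes first. SAP 2.1.2 names the further treatment as chemotherapy. Protocol 7.6 leaves care after withdrawal to patient and physician, with no waiting period. The safety follow-up visit (Protocol 6.2.6, at least 30 days after the last dose, with 14 more allowed) includes "Reporting of subsequent cancer therapy if applicable", and the end-of-treatment visit has the same item. SAP 10.2 plans Listing 16.2.5.7, "Further anti-cancer therapies", but nothing links it to the AE tables.

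For laboratory data, SAP 8.10.2 states: "The summaries will include all laboratory assessments collected from baseline assessment until 30 days after treatment discontinuation".

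For tumour response, by contrast, SAP 7.6.1 uses only assessments made before further antineoplastic therapy.

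**The concern.** A patient who stops TG4050 because progression calls for new treatment may begin that treatment within weeks, while every new adverse event is still being counted as treatment-emergent for TG4050. Cytopenia or another effect of chemotherapy that begins inside the 30 days would appear in the all-cause rows with nothing to show that a second treatment was on board.

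This matters because safety is the primary objective, there is no control arm, and the denominator is very small. The SAP deals with the same problem for tumour response but not for safety.

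**Working it through.** The documents state no figure on this point, and no formal sample size calculation, so there is nothing to reproduce. The check has four parts.

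**1. Is there a cut or flag?** The TEAE definition, the AE summary rule, the items of the AE listing, the overview rows and the laboratory section of the SAP were read together with Protocol 9.4.1. None ends the window at the next anticancer therapy or marks events after it. The only timing flags are for related AEs or SAEs, and for laboratory values, more than 30 days after treatment.

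**2. How long can the overlap be?** Let g be the days from last dose to the decision that new treatment is needed, and s the days from that decision to its start. Days of TEAE window left after the start = max(0, 30 − g − s).

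Planned dosing days after Day 43 are 43 + 21k, and planned scans (Protocol 8.2.1) are 43 + 63k, that is Days 106, 169, 232 and 295. Since 63 = 3 × 21, each scan day is also a dosing day. On the nominal schedule g is therefore about 0 (dose given on the scan day) to 21 (dose withheld). A 7-day slip makes it 28. The documents do not give s, so a range is assumed:

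- g = 0: s = 0, 7, 14, 21 leaves 30, 23, 16, 9 days.
- g = 21: s = 0, 7, 14 leaves 9, 2, 0 days.
- g = 28: s = 0, 3 leaves 2, 0 days.

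The overlap is thus 0 to 30 days.

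**3. What does one affected patient do to a row?** SAP section 4 gives 6 treated patients. One patient is 1/6 = 16.7 percentage points. Exact (Clopper-Pearson) 95% intervals, the method named in SAP 8.1:

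- 0/6 = 0% (0 to 45.9%)
- 1/6 = 16.7% (0.4 to 64.1%)
- 2/6 = 33.3% (4.3 to 77.7%)

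The full shift occurs only if the patient has no earlier event in that row. Protocol 1.5.2 lists injection site reactions among the common effects of this vector class, so the any-AE row may already contain most patients. The grade 3/4, SAE and fatal rows have more room to move. Event counts, which the SAP also tabulates, rise with every such event. The intervals show scale only, since the AE section plans counts and percentages.

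**4. Laboratory tables.** Blood count and biochemistry are scheduled at the end-of-treatment visit, within 7 days after treatment stops (Protocol 6.2.4). Neither is listed at the safety follow-up visit (6.2.6) or marked there in the flow chart (Appendix II B). The worst-grade shift tables can be affected only if the new therapy starts before the end-of-treatment sample, or through unscheduled samples.

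**The case against.** A fixed 30-day all-cause window is a defensible, conservative choice for a first-in-human viral-vector product. It keeps late reactions that an investigator wrongly rates as unrelated, and it matches the 30-day death criterion for suspending the study. This stands, and it is a good reason not to truncate the main tables.

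Attribution is also partly handled. The causality scale in Protocol 8.2.2.4 weighs other drugs, and the SAP overview has TG4050-related rows for AEs, SAEs, grade 3/4 AEs and AEs leading to discontinuation. With 6 patients, all AEs are listed with onset day, SAEs get narratives, and AEs are plotted by patient. A careful reader could find the overlap by hand. This limits the harm. It does not remove it: the primary endpoint is not confined to related events, the fatal-AE row has no related counterpart, and nothing in the tables prompts the comparison.

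It may also be argued that new therapy will seldom start so soon. Protocol 3.3 says second-line treatment is rarely begun while relapse is asymptomatic. That describes practice at relapse, before TG4050, but it does warn against assuming an immediate start. The synopsis bars concurrent antineoplastic therapy in the treatment period, which Protocol 8.2.3 extends to 30 days after the last dose for SAE reporting. Sections 7.5.1 and 7.6, and the collection of subsequent therapy at both closing visits, do not support reading this as a bar throughout the window.

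A reader might infer that second-line toxicity is in fact being counted and that the tables overstate the product's toxicity. The documents give no start dates or event counts, so they show only that it can be counted. A reader might also take 9 to 30 days as the overlap. That is the window left when progression is found, and any delay before the new therapy shortens it, possibly to zero.

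**Conclusion.** The gap holds as a missing flag. The all-cause TEAE summaries can include toxicity of second-line therapy that begins within 30 days of the last TG4050 dose, and the plan offers no means of separating it in the summary tables. The number of patients affected is unknown (0 to 6), and each moves a row by up to 16.7 points. The overlap is 0 to 30 days under assumed starting times.

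The TG4050-related rows are sound as far as investigator causality is correct. The wording of the laboratory section might suggest equal exposure of the shift tables, but the visit schedule confines it to end-of-treatment or unscheduled values. The analysis is descriptive and no decision rule rests on these rows. This is therefore a cheap improvement to the primary safety summary, not a defect that invalidates it.

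**What to change.** Keep the 30-day all-cause tables as they are, and add the following to SAP 8.10.1.2:

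- A derived flag for each TEAE with onset on or after the start of subsequent antineoplastic therapy, shown in the AE listings.
- A supplementary overview row or table of TEAEs with onset before that therapy. Events judged related to TG4050 stay in it whatever their timing.

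In 8.10.2, apply the same flag to any laboratory value after that date.

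First confirm that start dates are held for patients who stop for progression. Protocol 6.2.5 requires start and end dates of subsequent therapy, but in the follow-up of patients who stop for reasons other than progression or death. Protocol 9.5.4.3 collects dated medication records to 30 days after the last dose and should cover the others. Listing 16.2.5.7 is only a title in the SAP. The data review meeting before lock (SAP 7.2) is a suitable point to settle this.

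The cost is SAP wording, one derived variable and one extra table. No new data are needed if the dates are on file, and no event leaves the main tables.

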#### Serious Adverse Events (SAEs)

SAEs occurring after signing the Informed Consent Form (ICF) but before starting study treatment, including those observed in patients screened but not included will be listed separately from those occurring after treatment start.

AEs or SAEs occurring more than 30 days after administration of the last dose of TG4050 and evaluated by the investigator as related to TG4050 will be flagged.

##### a. Listings

All AEs will be listed with the following items:

- Patient Number
- Age
- Verbatim, Preferred term (PT) and System Organ class (SOC)
- Date of onset and date of end (study day)
- Duration of the AE in days
- Outcome (Recovered / Recovered with sequelae / Not recovered / Fatal / Unknown / Worsening)
- Evaluation of seriousness (Yes/No)
- Date of seriousness
- Intensity grade (Grade 1/ Grade 2 / Grade 3 / Grade 4 / Grade 5)
- Injection Site Reaction (Yes / No)
- Related to other study procedure (Yes /No)
- Dose Limiting Toxicity (Yes / No)

- Relation to TG4050 (Related/ Not Related)
- Action taken regarding TG4050 (None / Delayed / cancelled / Stopped / Not applicable)
- Action regarding the event (none, hospitalization....)

Moreover, the following sub-listings will be provided:

- Dose Limiting Toxicity AEs
- TG4050-related AEs
- SAEs
- TG4050-related SAEs
- AEs leading to discontinuation
- Grade 3/4 adverse events
- Fatal AEs
- Deaths
- Pre-treatment SAEs

b. Tables

An overview table will be provided with the number and percentage of patients for each of the following categories (the number of events will be also provided):

- with at least one AE
- with dose limiting Toxicity AEs
- with at least one AE related to TG4050
- with at least one injection site reaction
- with at least one AE related to other study procedure
- with at least one AE leading to treatment discontinuation
- with at least one AE related to TG4050 and leading to treatment discontinuation
- with at least one SAE
- with at least one SAE related to TG4050
- with at least one grade 3/4 AE
- with at least one grade 3/4 AE related to TG4050
- with fatal AE

---

 Related : reasonable possibility

 Not related : no reasonable possibility

The number and percentage of patients for each category listed above will be summarized in a frequency table by body system organ class (SOC) and preferred terms (PT) as per MedDRA dictionary. The number of events will be also summarized in the same table.

Table for AEs, AEs related to TG4050 will also be presented by grade and summarized in a frequency table by body system organ class (SOC) and preferred terms (PT) as per MedDRA dictionary.

Tables will be presented by SOC sorted in alphabetic order and PTs within SOC sorted by descending number of contents according to the overall column.

### 8.10.2 Laboratory abnormalities

The summaries will include all laboratory assessments collected from baseline assessment until 30 days after treatment discontinuation. All laboratory assessments will be listed and those collected more than 30 days after study treatment discontinuation will be flagged in the listings.

All laboratory values will be converted into SI units and will have a severity grade calculated using appropriate common terminology criteria for AEs (NCI-CTCAE, version 5). A listing of laboratory values will be provided by laboratory parameter and patient. A separate listing will display notable laboratory abnormalities (i.e., newly occurring CTCAE Grade 3 or 4 laboratory toxicities). The frequency of these notable laboratory abnormalities will be displayed by parameter. The shift tables using CTCAE grades to compare baseline to the worst post-baseline value will be produced for all relevant safety measures as described in the statistical analysis plan. Note that for parameters with two directions abnormalities (hypo/hyper), two tables will be presented.

### 8.10.3 Other safety data

Other safety data (e.g., vital signs, electrocardiogram) will be listed, notable values will be flagged, and any other information collected will be listed as appropriate. Any statistical procedures performed in order to explore the data will be used only to highlight any interesting comparisons that may warrant further consideration.

#### Vital signs

All vital signs (SBP and DBP in mmHg, pulse rate in bpm, temperature in °C and body weight in kg, BMI in kg/m^2) will be listed by patient. Vital signs at baseline will be summarized using descriptive statistics. All these results will be presented for SAF.

#### ECOG

ECOG performance status will be listed by patients. ECOG at baseline will be summarized using descriptive statistics. All these results will be presented for SAF.

## 9 DOCUMENT HISTORY

	Changes compared to previous version
Version 1.0 – 05AUG20	

Version 2.0 – 23SEP20	
Version 3.0 – 04JAN24	
Table 14.1.2.1 -7:9 CA-125 were removed
 
14.2 Efficacy data Tables were removed.
 
16.2.6-6:12 listings were removed.
 
14.2.2 -5:8 Figures were removed
 
EPP Listings/Tables were removed
 
CCI
 
[REDACTED]
 
[REDACTED]

## 10 LIST OF TABLES, FIGURES AND LISTINGS

### 10.1 Tables, figures and graphs

Table number	Title
14.1	DEMOGRAPHIC DATA
14.1.1	patients disposition
Table 14.1.1.1	Screen failure and non-inclusion reason – SCR
Table 14.1.1.2	Study populations
Table 14.1.1.3	Summary of protocol deviations – SCR
Table 14.1.1.4	Summary of protocol deviations – SAF
14.1.2	Demographic and Baseline characteristics
Table 14.1.2.1.1	Demographic data and study entry characteristics – SCR
Table 14.1.2.1.2	Demographic data and baseline characteristics – SAF
Table 14.1.2.2	Relevant Medical History and current Medical Conditions – SAF
Table 14.1.2.3	Signs and symptoms at baseline – SAF
Table 14.1.2.4.1:2	Prior anti-cancer therapies – SCR/SAF
Table 14.1.2.5	Vital signs and clinical examination – SAF
14.2	EFFICACY DATA
14.2.1	CA-125 Evolution
Figure 14.2.1 – 1	Waterfall plot for best percentage change of CA-125 – SAF
Figure 14.2.1 – 2	Evolution of CA-125 between Screening period and Treatment period – SAF
14.3	SAFETY DATA
14.3.1	Displays of adverse events
Table 14.3.1.1	Summary of adverse events – SAF
Table 14.3.1.2	Number (%) of patients with adverse events by cohort - SAF
Table 14.3.1.3	Number (%) of patients with adverse events by grade – SAF
Table 14.3.1.4	Number (%) of patients with adverse events related to TG4050 by grade – SAF
Table 14.3.1.5	Number (%) of patients with injection site reactions by grade – SAF
Figure 14.3.1.6	Adverse events by patient – SAF
14.3.2	Listings of deaths, other serious and significant adverse events
Table 14.3.2.1	Adverse events leading to treatment discontinuation, listing – SAF
Table 14.3.2.2	Adverse events due to DLT, listing – SAF
Table 14.3.2.3	Serious adverse events, listing – SAF
Table 14.3.2.4	Serious adverse events related to TG4050, listing – SAF
Table 14.3.2.5	Grade 3/4 adverse events, listing – SAF
Table 14.3.2.6	Fatal Adverse Events, listing – SAF
Table 14.3.2.7	Deaths, listing – SAF
14.3.3	Narrative of deaths, other serious and certain other significant adverse events
14.3.4	Abnormal Laboratory Value (each patient)
Table 14.3.4.1	Laboratory parameters Grade 3-4, listing – SAF
Table 14.3.4.2.1	Laboratory parameters - Grade shift table from baseline to worst grade - Hematology – SAF
Table 14.3.4.2.2	Laboratory parameters - Grade shift table from baseline to worst grade - Biochemistry – SAF

